#### 2. Planned and emergent analyses

Many analyses will be conducted to address the study objectives and these are summarised below. As noted, the complexity of the data will certainly lead to the performance of emergent analyses. These will always be defined as such, against this DAP, in any presentations, reports or papers. All publications will be made with the (Altman & Moher, 2013) transparency statement which will apply to the distinction between *a priori* and emergent analyses as much as to all important issues to be acknowledged transparently.

The analysis timing has been designed in three tranches.

- The first tranche will focus on the baseline data for participants recruited during the first three years. The most important focus will be to establish the baseline distributions of variables that will be used later to measure change, the psychometric properties of

those measures, the differences between clinical centers, and any strong associations between baseline variables likely to raise issues about confounding in the subsequent analyses of change.

- The second tranche will contain all data collected by the end of October 2020: the endof the intensive data collection phase. When analysing these data, the focus will be on change: changes in sociodemographic variables (assessed annually) and clinical interventions but primarily changes in the key clinical outcome variables of the questionaire scores and BMI.
- The third tranche will add the follow-up information for all the participants recruited to October 2020 as and followed-up, where in continued clinical contact with the services, to November 2025. The main analyses for this tranche will largely follow the explorations of change, its diversity and its predictors as from the second tranche.

Here we present the a priori analyses planned for each objective and broken down by tranche.

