# 3. Primary objective: Effectiveness of ITAMITED as it is applied routinely in its natural context.

We will analyse effectiveness with three complementary analyses performed for data/analysis tranches 2 and 3.

(a) Baseline/termination change. This is has been the traditional focus of many existing explorations of effectiveness of treatment. We will report both mean change and also effect sizes reporting Cohen's d2 and dz (Cohen, 1988) (the ratio of mean change to baseline SD and the ratio of mean change to SD of change respectively) and report these with bootstrap CIs. As well as reporting the global aggregate mean shifts with bootstrap 95% CI for each score. We will report the regression of termination scores on baseline scores and the distributions of change scores.

We will explore the impact of baseline variables: gender, age, diagnosis, demographic

variables, medication use and service on change. These predictor effects will be explored entering them as predictors of termination scores/values in ANOVA models with attention paid to the almost certain violation of assumptions of the ANOVA and exploration of mitigation of those violations. As gender and age are such crucial variables in Eating Disorders (Eds) the effects of entering these as predictors (or analysing separately be gender) on effects of other variables will be reported.

To address individual change we will report the Jacobson plot of termination against baseline scores for all scores and report the RCSC breakdown of change on each measure where it is possible to define the CSC and RCI.

(b) Multilevel models (MLM) of rates of change. MLM allows analysis of change slopes across diverse durations of therapy/ascertainment and the method handles the nonindependence of observations arising from the repeated measures within participant appropriately. These analyses can give a much more nuanced picture of change than baseline/termination analyses while allowing exploration of the effects of the same predictors and covariates analysed in (a). As for (a), durations of therapy are not directly reflected in the analyses though in contrast to (a), all data across all durations of data collection are used rather than just the first and last values.

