We will analyse fit to linear, square root and log-linear transforms of time as these have been the most widely reported linearised change/time patterns in the literature. The analyses against the baseline predictors (as fixed predictors) noted above allow some exploration of heterogeneity of change trajectories against those measured variables. Diagnostics after overall MLM analyses will be considered with the earlier analyses (i.e. tranche 1 baseline analyses, and baseline/termination analyses from tranche 2 above) as possible indicators of subgroups differing fundamentally in pertinent statistical characteristics. These subgroup indications will inform analyses exploring these subgroups as possible indicators of mixture model population structures of change.

However, heterogeneity may also relate to variables not measured in this study. (There are a very large number of such potential predictors, no realistic study can measure them all.) In order to explore possible heterogeneity other than arising from measured predictors we will conduct two other analyses of change trajectories relating to MLM estimation: latent profile analysis (LPA) of change and nearest neighbour prediction of change.

There are two complicating issues that will have to be considered here. The first is that not all centres were active at the start of data collection so analysis will be checked for any impacts of this, i.e. confounding by centre. The other challenge arose from the coronavirus pandemic. Social distancing regulations forced all but inpatient therapy to online therapy for (currently one) period in 2020. Time profiles will be inspected carefully against dates as well as against time in therapy to check on the impacts of this and in order to decide how best to prevent this creating artefactual impacts on trajectory analyses.

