# 4. Evaluation of the care types (inpatient, day hospital, and outpatient).

As with diversity of change, this aim will be explored largely through baseline/termination change broken down by types of care and, if numbers are large enough (to be explored by simulation) also by MLM and survival analysis with type of care as predictor (tranches  $\underline{1}$ ,  $\underline{2}$  and  $\underline{3}$ ).

However, this is clearly not a simple predictor/response relationship and there are two main complicating issues: that participants can have multiple trajectories through types of care, and that the types of care offered will reflect clinical need/severity and, probably to a lesser extent, demographic issues including age, occupation and carer responsibilities.

We expect that only a minority of the participants will receive only a single type of care as almost all who start in inpatient or day hospital care will progress to a less intense type of care and inpatient care unless they are very late recruits (and even then, transitions will be seen in the second, follow-up, phase of data collection). Inpatient care will often be succeeded by day hospital care and that in turn by outpatient care. A further complication is that a subset of participants will have "upward" as well as "downward" transitions and the diversity of trajectories across types of care will only permit robust MLM if only the major and simplest trajectories are analysed treating levels of care as time dependent covariates. For this reason, analyses will be only of the "simple transitions" but presented with clear caveats about the dangers of extrapolating overconfidently to all future clients starting in any of the three care types without taking the real complexities of transitions into account.

The second challenge, that types of care offered will undoubtedly be affected by severity (hence probably strongly correlated with scores on measures) and by some aspects of demography, can only really be explored in terms of associations with scores and with

demographics at baseline by type of care, and for the categories of later care type transitions.

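### All the time shapes pre-specified for the multilevel change models are monotone and are carried to the 2025 follow-up, so the fitted rate of change can understate the in-treatment gain or mislead in either direction

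*SAP*

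**What the plan says.** Section 3 of the SAP (primary objective), part (b), plans multilevel models of rates of change. On the time axis it says "We will analyse fit to linear, square root and log-linear transforms of time", because "these have been the most widely reported linearised change/time patterns in the literature". No quadratic, spline or piecewise term is named. The same part says that "all data across all durations of data collection are used rather than just the first and last values", and that the length of therapy is not directly reflected in these models.

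Section 2 (planned and emergent analyses) extends the data in tranche 3 to participants "followed-up, where in continued clinical contact with the services, to November 2025". It adds: "The main analyses for this tranche will largely follow the explorations of change, its diversity and its predictors as from the second tranche". No further time shape is introduced there.

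Part (b) also plans model diagnostics, exploration of subgroups, latent profile analysis of change and nearest neighbour prediction. Secondary objective 3 treats the last two as an extension of the multilevel models. The SAP does not say whether they work on raw trajectories or on fitted slopes.

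**The concern.** Linear, square-root and logarithmic time are each monotone when used as the single time term. A random slope per participant does not change this, because each person's curve still only rises or only falls. Comparing the three by fit picks the best of three monotone curves.

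Two plausible courses are then described badly. One is improvement followed by partial or full loss. The other is fast early improvement followed by a long plateau, where the many late scores pull the fitted line flat and the intercept absorbs the early gain. In tranche 3 a single coefficient blends the treatment phase with whatever follows.

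The multilevel model is the one primary analysis that uses the intermediate scores, and secondary objective 3 relies on it entirely, together with its latent profile and nearest neighbour extensions. A distorted rate of change would carry into the predictor effects on that rate. A turning shape added after the data are seen would, under the SAP's own rule, have to be declared emergent.

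**Working it through.** The SAP gives no effect size, course, loss rate or visit schedule, so there is no figure to reproduce. What follows is a noise-free illustration on stated assumptions.

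**Assumed course (SD units, negative = improvement).** Up to month 9, y(t) = -(1 - exp(-t/3)) / (1 - exp(-3)), so y(0) = 0 and y(9) = -1.00. From month 9 to 21, a linear loss of L. After month 21, flat at -1 + L.

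**Assumed schedules.** Monthly throughout, or dense early (two-weekly to month 9, then 3-monthly).

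**Fit.** Least squares of y on a + b f(t), with f(t) = t, sqrt(t) or log(1 + t), one at a time. Fitted 9-month change = b [f(9) - f(0)]. The true value is -1.00 in every row.

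| Observed to | L | Schedule | Linear | Square root | Log |
|---|---|---|---|---|---|
| 60 months | 0.50 | monthly | +0.04 | +0.10 | +0.12 |
| 60 months | 0.50 | dense early | +0.03 | +0.05 | 0.00 |
| 60 months | 0.25 | monthly | 0.00 | -0.03 | -0.11 |
| 60 months | 0.25 | dense early | -0.02 | -0.10 | -0.22 |
| 60 months | 0 | monthly | -0.04 | -0.17 | -0.34 |
| 60 months | 0 | dense early | -0.07 | -0.25 | -0.43 |
| 36 months | 0.25 | monthly | -0.02 | -0.12 | -0.24 |
| 36 months | 0.25 | dense early | -0.06 | -0.24 | -0.39 |

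The fitted intercept at 60 months is -0.63 to -0.76 for L = 0.50 and -0.38 to -0.81 for L = 0. The true starting value is 0. The missing gain has moved into the intercept.

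**Separating the causes.** The L = 0 rows have no loss at all, yet the fitted gain is still less than half the true one. So much of the shortfall comes from a long plateau after fast early change, and the rest from the loss.

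**Sensitivity to the gain shape.** With a linear gain to month 9, the best case at 36 months with L = 0.25 is -0.58 (log, dense early).

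**Only a minority losing ground.** Least squares is linear in y, so on a common schedule a mixed cohort is a weighted average of the rows. With 20% at L = 0.50 and 80% at L = 0 over 60 months, monthly linear gives 0.8(-0.04) + 0.2(0.04) = -0.02, and dense-early log gives 0.8(-0.43) + 0.2(0.00) = -0.34. The other four combinations lie between.

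**Direction of error.** A second set of courses has a linear gain of 1 unit to a turning point at 25%, 50% or 75% of 36, 60 or 96 months, then full loss. Visits are every 3 months, or monthly to month 12 and 6-monthly after that. The true first-to-last change is 0. The fitted change runs from +0.46 (apparent net worsening) to -0.83 (most of the gain apparently kept). For a turning point at half of 60 months with 3-monthly visits it is 0.00 (linear), -0.23 (square root) and -0.43 (log), with R² of 0.00, 0.04 and 0.12. A quadratic on the same data has R² 0.94.

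**Does a flexible shape help?** In the main example (60 months, L = 0.50), a restricted cubic spline with knots only at 3, 9 and 18 months gives a 9-month change of -0.23 (monthly) and -0.44 (dense early), because it is forced to be straight from month 18 onward. Adding boundary knots at 0 and 60 months gives -0.90 and -0.88.

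**The case against.** The strongest reply is that the SAP does not rest effectiveness on this slope. It plans three complementary analyses. Part (a) reports mean baseline/termination change, two effect sizes, change distributions, Jacobson plots and reliable and clinically significant change, none of which depends on a time shape. Part (c) covers time to termination. This stands: how much people change by termination is answered elsewhere, and it would be wrong to say the primary question hangs on the slope alone. But part (a) uses first and last values only and does not describe the course between them.

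A reader might infer that the SAP expects scores to worsen. It does not say so. The nearest text, in secondary objective 4, is that "a subset of participants will have 'upward' as well as 'downward' transitions". That concerns care type, which the same section ties to severity and also to demographic circumstances. A reader might also infer that improvement followed by loss will always appear as no change. The calculations do not support that, since the error can run either way. Nor does the SAP say that tranche 3 exists to test whether gains last.

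It can also be said that diagnostics, subgroup exploration, latent profiles and nearest neighbour prediction might reveal turning courses, that time profiles will be inspected, and that emergent analyses are allowed. This stands in part. The diagnostics are aimed at subgroups and the inspection at pandemic artefacts, while the inputs to the profile and neighbour methods are unspecified. That these methods inherit a monotone shape is a possibility, not a fact. Care level as a time-dependent covariate could bend a curve, but only for the simple care transitions to which those analyses are limited.

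Finally, the SAP calls itself exploratory and a shortened version of a larger document. That argues against demanding fine detail, but not against naming one more shape in a list that already names three.

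**Conclusion.** The point holds in this form. Every time shape pre-specified for the multilevel models is monotone as a single term, the plan carries them largely unchanged to November 2025, and nothing separates in-treatment from later change. They cannot represent gain followed by loss, and they fit an early gain with a long plateau poorly.

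On the assumed courses observed to 60 months, the fitted 9-month change lies between +0.12 and -0.43 SD against a true -1.00. At 36 months with a quarter of the gain lost, the best case is -0.39, or -0.58 if the gain is linear. First-to-last change can be wrong in either direction. The sizes rest on assumed courses, schedules and complete observation, and on reading the three transforms as alternatives rather than terms entered together. The limitation itself follows from the shapes and needs none of these figures. It affects the rate-of-change results and what is built on them, not the baseline/termination results.

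**What to change.** 1. In tranches 2 and 3, pre-specify at least one flexible shape alongside the three transforms. A restricted cubic spline of time since entry would serve, with boundary knots at entry and end of follow-up and interior knots fixed in advance from the distribution of visit times. The boundary knots matter, as the last calculation shows.
2. In tranche 3, add a piecewise model with a break at first termination of treatment. Report the in-treatment rate separately, and present the later slope only as describing those still in contact with the services. It cannot show whether the whole cohort keeps its gains.
3. State that latent profile and nearest neighbour analyses use raw trajectories or the flexible shape, not slopes from the monotone fits.

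The cost is a few sentences in the SAP, a few more model terms, and possibly a simpler random-effects structure if the fuller one does not converge.

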# Secondary objectives:

### 1. Describe the study participants.

To establish the baseline distributions of variables (i.e., BMI, CORE, EAT-26/ChEAT-26, and BITE) that will be used later to measure change (tranche 1). The aims are:

- To describe the distributions of scores at baseline on the change measures and how these relate to other variables:
  - demographic variables, primarily age and gender;
  - o clinical variables primarily diagnosis, care type and medication and,
  - both because of the interest in this within ITA, and for the MLM analyses
    of change (above) and the differences between clinical centres.

### 2. Study the psychometric properties of the self-report measures.

To explore the baseline, cross-sectional psychometric properties of the self-report measures (tranche 1). The analyses will be as follows.

 Acceptability in terms of omitted items. Where measures have recommended prorating for some proportion of missed items the proportions proratable will be reported. If omission rates are high the possible effects of prorating, and the possible biases if omission is associated with any particular demographic or clinical variables, or tends to occur at higher or lower scores across the completed items will be note.

- Floor and/or ceiling effects for items.
- Internal reliability (Cronbach alpha (Cronbach, 1951) and McDonald's Omega (Revelle & Zinbarg, 2008) of scores both for the total participant group completing all items, but also by gender and diagnostic groups and by age for the young participants (as there is evidence (e.g. Twigg et al., 2016) that reliability, as well as score distributions, can vary importantly and statistically significantly with gender and age through adolescence). There has been much argument against the use of Cronbach's alpha, much of it accusing it of doing things Cronbach was careful in 1951 to say it didn't do, fundamentally these criticisms are that it can both underestimate and overestimate classical test theory (CTT) reliability, the latter particularly when a measure is not unidimensional. McDonald's omega corrects the latter issue particularly but alpha has been, and may remain, the dominant statistic reflecting internal reliability hence we will report both.
- Construct validity in terms of factor analyses within and across measures. We 0 believe that factor analytic methods are often overvalued when applied to short, broad coverage measures of diverse problems, measures designed as much to be good within-individual reflections of change as to be good between-individual comparators. However, both in clinical practice and research all the self-report measures used in the study are used both for comparisons across individuals and to measure change over time hence it is important, as with reporting the internal reliability, to explore factor structure. The within measure exploration will use confirmatory factor analysis (CFA) where either there are widely used scale scores for the measure or where there has been debate in the literature about whether a measure (or scale/score) is unidimesional or has more factors of interpersonal difference. As the indicators (items) are short ordinal scales and as the latent variables are almost certainly not Gaussian in distribution, we will use both maximum likelihood (ML) and diagonally weighted least squares (DWLS) (Li, 2016; Rhemtulla et al., 2012) estimation and appropriate scaled/robust fit

statistics (Satorra & Bentler, 2010) for the estimation method. Assuming the DWLS and robust fit statistics give better fit these will be reported with a note about the ML fit. If numbers allow (n > 250) separate analyses will be conducted by gender, age and diagnosis.

We will explore factorial measurement invariance across first and second completions (exempting items clearly impacted by the restrictions of hospitalisation). We will also explore invariance between groups by gender, sensible age groups (determined partly by cell sizes, here again n > 250) and diagnoses (again, restricted by sufficient cell sizes). For both temporal and between group analyses we expect only quite low levels of invariance as we believe there are very real changes and differences in structure, hence the focus will be more on the magnitude of the impacts on scores of the invariance rather than whether statistically significant invariance is or is not present. If fit to the scale design is particularly bad, exploratory factor analyses will be conducted and reported.

As well as within-measure analyses, we will also conduct across-measure factor analyses as these allow construct validity to check on where one might expect shared factor structure (i.e. for (Ch)EAT and BITE) or might expect largely unrelated factor structure (i.e. between (YP-)CORE and both (Ch)EAT and BITE). These analyses will be CFA by design structure and EFA if fit to design structure is clearly very poor.

- If some measures/scores show clear fit to unidimensionality, we will conduct Item Response Theory (IRT) analyses to identify cutting points and potential evidence that the conventional scoring of the measures may be suboptimal for cross-sectional comparisons.
- Convergent validity between related measures (EAT-26/CHEAT-26 and BITE) and convergent and divergent validity between them and diagnoses and BMI. These are more conventional explorations than the item level across-measure factor analyses noted above. We will explore scatterplots for marked non-linearity or

clearly non-zero intercepts and, assuming there are not major issues of those kinds, will report Spearman rho and Pearson R correlations with bootstrap confidence intervals. Reporting both correlations maximises comparability with existing literature as Spearman correlations have often been reported in the past, before the widespread availability of bootstrapping, as score distributions are generally not Gaussian. If numbers allow (n > 80) separate analyses will be conducted by gender, age and diagnosis.

Divergent validity/confounding against gender, age, first language, education.
 Distributions will be compared by groups (with sensible age groups) and the simple scattergrams against age inspected. Unless clearly inappropriate Pearson correlations with age, and mean differences by groups, will be reported with bootstrapped CIs.

To explore the psychometrics of change (tranche  $\underline{2}$  and  $\underline{3}$ ):

- Where participants have sufficient completed measures (n > 20) we will to apply P-technique estimation of Cronbach's alpha within individuals, within and across measures. For the small number of participants with the larger number of sufficient completions (n > 40) we will also explore P-technique "factor" structure (actually Principal Component Analyses (PCA)) to show the structures that emerge where the sequences of completed measures within individuals allow this.
- As well as individual P-technique we will use "chained P-technique" to look for shared intraindividual factor structure of change. These methods are essentially those of the exploration of measurement invariance by CFA with repeated completions over time within individuals being compared for structure.

